4 BACKGROUND AND SIGNIFICANCE

A major pathological hallmark of AD is the appearance in the brain of senile plaques composed of aggregated forms of A β , which is a proteolytic product of APP. Both accumulation of A β and other pathological changes, such as development of neurofibrillary tangles, synaptic loss and brain atrophy, are thought to occur one or two decades prior to overt dementia. Soluble A β oligomers have been demonstrated to show toxicity in vitro and in vivo and represent a target for drug development in AD. Recent research has shown that soluble forms of phosphorylated tau (p-tau) and α SYN may also contribute to neuronal loss and that AD as well as Parkinson's Disease carry a high load of inflammation and microglia activating factors that contribute to neurodegeneration.

For small molecules that target A β protein metabolism or other key biochemical pathways in AD, studies using CSF and plasma sampling in humans can provide data to demonstrate that a drug crosses the blood-brain barrier and engages the relevant target, and to describe the relationship between blood levels and central nervous system (CNS) effects. Repeated sampling through a lumbar CSF catheter for up to 36 hours, and the additional technique of SILK™ to measure parameters such as fractional synthesis rate of A β , can help guide the development of drugs targeting A β .

Posiphen is the (+) enantiomer of phenserine, an AChE inhibitor which had been tested in several AD studies without significant evidence of efficacy. Preliminary data shows that Posiphen is affected by food; however, when the drug is taken in a series there is no effect on the PK analyses results. However, the failure of those studies with phenserine may have been related to the formulation, which is significantly affected by food. While phenserine inhibits AChE, Posiphen has no AChE activity itself and develops some activity in vivo with the metabolism to N1-bisnorposiphen. In vivo phenserine is about 200 times more potent in regards to AChE activity than Posiphen, when metabolized to N1-bisnorposiphen.

Posiphen has been found to significantly reduce soluble APP and A β as well as tau, p-tau and α SYN in the rodent brain and in human CSF. In preliminary studies in animals and humans, inhibition of APP, A β , tau, p-tau and α SYN occurs at levels 6 to 10 times lower than the levels causing cholinomimetic effects.

Posiphen is thought to act at the 5'UTR of the APP mRNA and lowers APP and A β protein levels in animal models, and decreased sAPP levels in human CSF. Preliminary data suggests that these effects are achieved via the same mechanism of binding to the 5'UTR of mRNAs and inhibiting their translation.

As Posiphen is thought to inhibit the synthesis of APP, as well as other neurotoxic aggregating proteins, it might have a broader spectrum of activity and protect neurons and have a disease-modifying effect in AD as well as other neurodegenerative disorders.

CSF Sampling and SILK™

Sampling CSF repeatedly for as long as 36 hours through a lumbar catheter had been initially used in a few studies related to AD treatment during the 1990s ([Cutler 1998](#)). The technique has gained greater utility in relation to measuring pharmacological effects on A β with the addition of SILK™, a technique developed by Dr. R. Bateman and colleagues at Washington University ([Bateman 2006](#)). This technique involves placement of a lumbar CSF catheter, followed by intravenous infusion of $^{13}\text{C}_6$ -labeled “heavy” leucine for 9 hours. Leucine is an essential amino acid that undergoes active transport into the brain. $^{13}\text{C}_6$ leucine is non-radioactive, harmless to humans and the environment, and is physically identical to unlabeled ($^{12}\text{C}_6$) leucine except for an additional proton difference in the mass of the amino acids. The leucine is incorporated into a fraction of newly synthesized proteins throughout the body, including the brain, which are secreted into the CSF. Samples of CSF are collected and A β is immune-precipitated from the CSF, and the ratio of A β containing $^{13}\text{C}_6$ -leucine to that containing unlabeled leucine is measured using mass spectrometry. During hours 4-12 after start of the leucine infusion, the fraction of labeled A β in the lumbar CSF increases, reaching a maximum of about 10%. The slope (change in % labeled A β /time) is called the fractional synthesis rate (FSR) and is a measure of the rate of A β synthesis in the brain. During late stages of the catheter procedure (hours 24-36), the fractional % of A β that is labeled decreases linearly, and the slope is measured to calculate the fractional clearance rate (FCR). Using this method, Bateman and colleagues estimated that A β has a rapid FSR and FCR in CSF.

As part of their CSF sampling studies, Bateman and colleagues measured CSF A β hourly for 36 hours in healthy adults and participants with AD. They found that CSF A β in normal subjects fluctuate from hour to hour, in a circadian pattern, and to a much greater extent than in participants with AD ([Huang 2012](#)). This variability complicates the design of studies in which CSF is sampled in a serial manner through a single lumbar puncture before and after treatment from the same person.

In this study $^{13}\text{C}_6$ -leucine will be infused during the CSF catheterization procedure. CSF samples will be collected for mass spectrometry analysis of A β 40 and A β 42 to see if treatment with Posiphen decreases CSF levels of A β 40 and of sAPP β measured initially by mass spectrometry.

During the leucine infusion, participants must comply with a low leucine diet – approximately 1500 mg or less of leucine per day (refer to Appendix 4, Sample Low Leucine Menu). The kitchen on site will be responsible for preparing low leucine meals and snacks while maintaining a food journal for each subject. Subjects who break the low leucine diet will not be excluded from the study, since this will not be evident until the leucine analyses are completed.

At the end of the study, all unused leucine should be returned to C2N.

Study population: The study will be conducted in participants with a clinical profile consistent with early AD including MCI due to AD and mild Alzheimer’s disease, consistent with the core clinical criteria outlined in the NIA-AA guidelines (2011), MMSE inclusion score between 17 – 30 (inclusive), Clinical Dementia Rating (CDR) global score of 0.5 with a memory score of 0.5 or

greater, or global score of 1.0, and by the presence of a CSF A β 42/ A β 40 ratio less than 0.131 consistent with AD (as measured by C2N at screening). All subjects will have a screening lumbar puncture to measure the CSF A β 42/40 ratio. These biomarkers can support a diagnosis of AD. CSF will be stored to allow analysis of baseline (pre-treatment) levels of larger biomarkers.

Dose selection: Posiphen will be tested at doses of 60 mg QID, 60 mg BID (120 mg total daily), and at 60 mg TID (180 mg total daily). Whereas the plasma t $\frac{1}{2}$ of Posiphen has been determined to be 5 hours, the CNS t $\frac{1}{2}$ is estimated to be over 12 hours, allowing that once daily dosing may be feasible. However, previous studies indicated that likely cholinergic adverse events are mostly driven by Cmax. In particular, in the SAD study significant nausea, vomiting and dizziness occurred at a single dose of 160mg. In the MAD study 40mg QD (=160 mg/day) was well tolerated. Thus, the same total daily dose is better tolerated if divided into several doses. The use of multiple doses compared to once a day in this study will help evaluate the PK/PD relationship in the context of tolerability of different administration schemes.

Study Design: This study is designed as a Phase 1b multicenter, randomized, double-blind, placebo-controlled study evaluating safety, tolerability, PK and PD of 23-25 days exposure to multiple ascending doses of Posiphen in up to 24 participants with a clinical profile consistent with early AD including MCI-AD or Mild AD with the following planned doses:

- 60 mg QD (1x60mg)
- 60 mg BID (2x60mg)
- 60 mg TID (3x60mg)

Each dose group will include 8 subjects, 5 randomly assigned to Posiphen and 3 randomly assigned to placebo.

There is some risk of excess cholinergic adverse events given that some subjects will be included who are on cholinesterase inhibitor treatment for Alzheimer's disease which may become additive with the first metabolite of Posiphen (N1-norPosiphen) that has anticholinesterase properties.

Therefore, each dose group will be completed and evaluated for safety and tolerability by the standing ADCS DSMB before the next dose group is initiated.

Subjects who do not tolerate study drug during the initial 3-week at home treatment period will be discontinued and replaced by new subjects. If two subjects at a given dose are discontinued due to adverse events, no additional subjects will be added at this dose level until a safety review has been conducted. The safety committee will determine the appropriate dose level for additional subjects. The safety committee has the option to change the allocation of future patients to active drug versus placebo based on statistical advice to maintain an appropriate balance between placebo subjects and subjects on active drug.

Outcome measures to assess pharmacodynamics: Transcriptional inhibition of the APP gene will result in decreased production of APP, which may be reflected by decreased secretion of the processed parts fragments of APP, namely sAPP and A β , in CSF. We have selected A β 40 as a primary outcome measure because it has a relatively high concentration in CSF and is unaffected by the deposition of A β as plaques in the brain, which will be present in the study population. We also will measure secreted forms of APP (sAPP α and sAPP β) and levels of tau in CSF as secondary outcome measures. sAPP reflects processing of APP by α -secretase to

produce sAPP α and β -secretase (BACE) to produce sAPP β . Tau levels are being measured since tau transcription may be under the regulation of a similar IRE that may also be affected by Posiphen treatment.

Safety outcome measures: Reports of adverse events (AEs) and serious adverse events (SAEs) during exposure to Posiphen will be collected to evaluate if there are any significant clinical safety issues for the study population. All SAEs occurring up to 30 days after last study drug administration that are considered drug-related must also be reported. Extensive clinical and laboratory safety data already exist for Posiphen, therefore, this approach will be sufficient in the proposed study.

Clinical and cognitive assessment measures: Although clinical benefit is unlikely due to the short duration of this study, standard cognitive measures (MMSE, Logical Memory subtest of the Wechsler memory Scale (Story 1 only), and ADAS-cog) will be collected to describe the study cohort, which allows comparison to subjects in other clinical trials. It is predicted that cognition will remain stable over the course of drug exposure; however, this will be assessed formally in clinic.

5 POTENTIAL RISKS AND BENEFITS OF INVESTIGATIONAL PRODUCT AND STUDY PROCEDURES

5.1 Risks and Benefits Associated with Posiphen or Placebo

There are no benefits to the subjects other than receiving medical and selective cognitive evaluations.

The clinical investigator should advise all potential subjects of the possibility of unexpected side effects and carefully evaluate each person exposed to Investigational Product for possible AEs.

Side effects to placebo are not uncommon but are obviously not due to a pharmacological agent as an industry standard placebo (non-lactose compound) will be provided. The placebo used for the study consists of microcrystalline cellulose which is generally recognized as safe (GRAS), with no known side effects anticipated.

In clinical studies to date, Posiphen has been well tolerated with single doses of 80 mg or less and QID doses of 60 mg. A higher single dose of 160 mg was associated with an increased incidence of nausea and vomiting, potentially cholinergic based side effects, which resulted in the decision not to test higher single doses. Please refer to table below from the single, ascending dose study, which included healthy men and women:

Table 5.4-1: Summary of Adverse Events in More Than One Subject Per Treatment Group (Males and Females Combined) Study AX-PO-101

Body System Adverse Event ^a (Preferred Term)	Number (%) of Patients in Treatment Group (n = 72)						All Posiphen (n = 60)	Placebo (n = 12)
	10 mg (n = 10)	20 mg (n = 20)	40 mg (n = 10)	80 mg (n = 10)	160 mg (n = 10)			
All AEs, mild	2 (20.0)	4 (20.0)	1 (10.0)	3 (30.0)	3 (30.0)	13 (21.7)	2 (16.7)	
All AEs, moderate	1 (10.0)	2 (10.0)	0 (0)	0 (0)	4 (40.0)	7 (11.7)	1 (8.3)	
All AEs, severe	0 (0)	1 (5.0)	0 (0)	0 (0)	0 (0)	1 (1.7)	1 (8.3)	
Gastrointestinal Disorders								
Nausea	0 (0)	2 (10.0) ^b	0 (0)	0 (0)	4 (40.0)	6 (10.0)	0 (0)	
Vomiting	0 (0)	0 (0)	0 (0)	0 (0)	3 (30.0)	3 (5.0)	0 (0)	
General Disorders and Administration Site Conditions								
Feeling hot	0 (0)	2 (10.0)	0 (0)	0 (0)	0 (0)	2 (3.3)	0 (0)	
Investigations								
Heart rate increased	2 (20.0)	1 (5.0)	0 (0)	0 (0)	0 (0)	3 (5.0)	2 (16.7) ^b	
Nervous System Disorders								
Dizziness	1 (10.0)	4 (20.0) ^b	1 (10.0)	3 (30.0)	4 (40.0)	13 (21.7) ^b	3 (25.0) ^b	
Fainting ^c	1 (10.0)	1 (5.0)	0 (0)	0 (0)	0 (0)	2 (3.3)	1 (8.3)	
Vascular Disorders								
Orthostatic hypotension	0 (0.0)	1 (5.0) ^b	0 (0)	0 (0)	0 (0)	1 (1.7) ^b	1 (8.3) ^b	

^a = A subject may have experienced more than one AE in more than one category at more than one severity, each counted as a separate event.
^b = Includes at least one AE reported as severe.
^c = *Dizziness* is the preferred MedDRA term, which encompasses descriptive terms *fainting*, *dizzy*, and *lightheadedness*.

Aside from nausea and vomiting, which are well-known responses to treatment with ChE inhibitors, the only consistent pattern of AEs entailed dizziness/fainting, headache, and reduction in total serum protein. These effects were seen to varying degrees at all doses of Posiphen and also in the placebo group. There was a tendency, but no definitive pattern of increased incidence of AEs with increasing dose of Posiphen. There have been no SAEs in prior clinical studies with Posiphen.

Definitive reproductive and developmental toxicity studies have not been conducted with Posiphen. As a result, women of childbearing potential will be excluded from participating in this study.

5.2 Risk/Benefit Associated with Blood Collections

Phlebotomy is associated with mild to moderate discomfort due to piercing of the skin. This can be minimized with the use of a well-trained phlebotomist/nurse. Sometimes the blood draw site may become discolored with a “bruised” appearance that is transient and not painful. Rarely, the blood draw site may become infected and require antibiotic treatment.

5.3 Risk/Benefit Associated with SILK™ Procedure and CSF Sampling

The most frequent adverse event associated with these studies was post-lumbar puncture headache. This was successfully managed by blood patching if a participant is unresponsive to orally administered fluids and/or caffeine.

Other potential risks include meningitis, pain or tingling sensation in the lower extremities, temporary eye weakness or double vision, infection or bleeding at the site of catheter insertion, pain at the site of insertion, backache, epidural or subdural bleeding, infection, paralysis and potential injury to the nerve root.

In studies conducted at C2N Diagnostics and at Washington University, the rate of post-lumbar puncture headache requiring a blood patch is about 10% in older individuals ([name], personal communication).

5.4 Risk/Benefit Associated with Investigational Drugs Intended to Reduce β -amyloid in the Brain

In 2010, Food and Drug Administration (FDA) sent a notice to all sponsors of investigational compounds that are intended to treat Alzheimer's disease by reducing A β in the brain of the occurrence of imaging abnormalities believed to represent cerebral vasogenic edema. These imaging abnormalities were noted in a study of a monoclonal antibody (Salloway, 2013) and were, in the majority of instances, asymptomatic, and their presence was detected by routine brain magnetic resonance imaging (MRI). Symptoms, when present in association with such imaging abnormalities, were reported to include headache, worsening cognitive function, alteration of consciousness, seizures, unsteadiness, and vomiting. In most instances, the occurrence of such imaging abnormalities, even when symptomatic, did not require treatment beyond discontinuation of the investigational compound, with imaging abnormalities then resolving. Infrequently, high-dose steroid therapy was administered in the presence of prominent symptoms.

More recently (2014), FDA has determined that, following a comprehensive review of existing data, development programs investigating use of a monoclonal antibody that targets β -amyloid (regardless of mechanism) must incorporate serial clinical and MRI monitoring. However, development programs for small molecules that target A β are only required to inform investigators of the potential risk of cerebral vasogenic edema including its imaging manifestations, accompanying clinical signs and symptoms, and appropriate management should symptomatic cases occur. Informed consent documents for these programs should also include a description of the manifestations of cerebral vasogenic edema, including its possible symptoms (i.e., headache, worsening cognitive function, alteration of consciousness, seizures, unsteadiness, and vomiting).

6 SAMPLE SIZE AND STATISTICAL PLAN

A sample size of up to 24 subjects (5 randomized to Posiphen and 3 randomized to placebo per treatment group) is planned across 3-6 clinical research centers.

6.1 Randomization

Subjects who have signed an informed consent and meet screening eligibility requirements will be randomly assigned to receive 60 mg Posiphen daily or placebo (with an allocation of 5 on Posiphen, 3 on placebo) by a stratified, random permuted blocked treatment assignment method, stratified by site. Following dosing of the initial 8 subjects and review of safety and tolerability, the next dose group will be 60 mg BID Posiphen or placebo (5 on Posiphen, 3 on placebo). Following the dosing of this group of 8 subjects and review of safety and tolerability, the next dose group will be 60 mg TID Posiphen or placebo (5 on Posiphen, 3 on placebo).

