1 PROTOCOL SYNOPSIS

PROTOCOL TITLE	A Multicenter, Randomized, Double-Blind, Placebo-Controlled Ascending Dose Study to Evaluate the Safety, Tolerability, PK and PD Effects of Posiphen® in Subjects with Early AD
PROJECT DIRECTORS	[name]. and [name].
COORDINATING CENTER	Alzheimer's Disease Cooperative Study (ADCS)
STUDY DESIGN	
A Phase 1b multicenter, randomized, double-blind, placebo-controlled study evaluating safety, tolerability, PK and PD of 23-25 days exposure to multiple ascending doses of Posiphen in up to 24 participants with a clinical profile consistent with early AD including Mild Cognitive Impairment due to AD (MCI-AD) or Mild AD with the following planned doses:
 
 • 60 mg Once a Day (QD) (1x60mg) • 60 mg Twice a Day (BID) (2x60mg) • 60 mg Three Times a Day (TID) (3x60mg) 
Each dose group will include 8 subjects, 5 randomly assigned to Posiphen and 3 randomly assigned to placebo.
 
Each dose group will be completed and evaluated for safety and tolerability by the standing ADCS Data Safety Monitoring Board (DSMB). The ADCS DSMB will determine whether to approve dose escalation.
 
Subjects who do not tolerate study drug during the initial 3-week at-home treatment period will be discontinued and replaced by new subjects. If two subjects at a given dose are discontinued due to adverse events, no additional subjects will be added at this dose level until a safety review has been conducted. The safety committee will determine the appropriate dose level for additional subjects. The safety committee has the option to change the allocation of future patients to active drug versus placebo based on statistical advice to maintain an appropriate balance between placebo subjects and subjects on active drug.

DURATION OF STUDY PARTICIPATION	Each subject will have up to a 42-day screening period, followed by approximately 21-23 days of treatment at home, and an in-clinic visit that includes treatment and a 36-hour lumbar puncture (LP) Stable Isotope Labeling and Kinetics (SILK™) procedure.
SUMMARY OF INVESTIGATIONAL PRODUCT	Posiphen 60 mg QD, 60 mg BID or 60 mg TID, or placebo capsules taken orally for up to 25 days.

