2.2 Secondary Aims

Aim 4: To implement a multicenter lumbar CSF catheter study employing standardized methodology and SILK™ technology. The following criteria will be evaluated as outcomes to determine feasibility:

- Enrollment comparisons of research subjects at each of the 3 sites
- Adequacy of sample collections to permit analyses of PK and PD effects of Posiphen
- Subject satisfaction questionnaires
- Comparison of protocol deviations and variances in data between the sites

Aim 5: To assess the PD effects of treatment with Posiphen versus placebo on the levels of the following biomarkers in CSF of subjects with early AD:

- A β 38 and 40
- sAPP α
- sAPP β
- T-tau protein (T)

Aim 6: To assess whether there are short-term cognitive and/or neuropsychiatric effects of Posiphen in subjects with early AD, either positive or negative.

- ADAS-Cog12
- MMSE
- Neuropsychiatric Inventory (NPI)

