The primary outcome measure of Fractional Synthesis Rate (FSR) of Abeta 40 will be compared across all Posiphen treated groups to placebo. A linear regression model will be used to evaluate treatment effects on the FSR Abeta 40, with age and gender as covariates. Quality control of samples for the FSR 40 will be ascertained to determine sufficiency of the sample values prior to this regression analysis.

A secondary analysis will test for possible dose group by treatment interaction.

Exploratory analyses will include PK AUC correlation to Abeta 40 FSR and other SILK measured analytes (Abeta 38, 42, ratio 42/40, total Abeta peptides) including absolute synthesis and clearance.

C2N will analyze Beta Amyloid 40 (Ab40).

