5.2 Secondary Aims

5.2.1 Aim 1

To implement a multicenter lumbar CSF catheter study employing standardized methodology and SILK™ technology. The following criteria will be evaluated as outcomes to determine feasibility:

Enrollment comparisons of research subjects at each of the 5 sites. Screen failure rates will be evaluated by cause, by number and by site. Demographics will be described across sites. There will be comparison of protocol deviations and sampling results between the sites. Adequacy of sample collections to permit analyses of PK and PD effects of Posiphen during the SILK will be tabulated. Description of the adequacy of SILK sampling, Pk and PD during the confinement visits will be undertaken with comparisons across sites.

Research Satisfaction Questionnaires: Descriptive ratings of participants in response to the research study will be undertaken across visits including baseline and post-confinement when this questionnaire was administered. The responses on the survey will be grouped and compared to address the experience across the trial with characterization of the most frequent terms. Cross tabulations and shift tables will be used to address the response to the SILK procedure through its categorical variables and its influence on participant satisfaction. We will explore whether there is any indication of an effect of treatment on these participant profiles.

5.2.2 Aim 2

To assess the PD effects of treatment with Posiphen versus placebo on the levels of the following biomarkers in CSF of subjects with early AD: Ab 38 and 40, sAPPa, sAPPb, total tau protein.

Mean changes in these biomarkers will be compared across treatment arms between baseline and day 21 time 0 prior to the leucine infusion pooling all participants treated with Posiphen vs placebo across cohorts. Linear regression modelling will allow the comparison of mean change scores in the analytes between the active and placebo groups while adjusting for covariates including age, gender, MMSE at baseline, and Apo-e status as well as armcode and dose cohort and cohort-by-armcode interaction.

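### Site-stratified blocks do not secure 5:3 in each dose cohort of eight, and the primary FSR model leaves out the cohort within which treatment is randomised

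*Protocol*

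**What the plan says.** The Protocol Synopsis sets the allocation: "Each dose group will include 8 subjects, 5 randomly assigned to Posiphen and 3 randomly assigned to placebo". Protocol 6.1 and SAP 3 repeat the 5 and 3 for each of the three successive cohorts and give the method as "by a stratified, random permuted blocked treatment assignment method, stratified by site". Dose cohort is not named as a stratum.

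The number of sites varies. Protocol 6 says the sample "is planned across 3-6 clinical research centers", and SAP 4.1 agrees. Protocol 2.2 lists "Enrollment comparisons of research subjects at each of the 3 sites", and SAP 5.2.1 lists "Enrollment comparisons of research subjects at each of the 5 sites".

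For the primary FSR outcome, SAP 5.1.3 pools all Posiphen subjects against placebo in a linear regression of "treatment effects on the FSR Abeta 40, with age and gender as covariates". Cohort enters for FSR only afterwards: "A secondary analysis will test for possible dose group by treatment interaction". The secondary CSF biomarker model in SAP 5.2.2 does adjust for cohort, with covariates that include "Apo-e status as well as armcode and dose cohort and cohort-by-armcode interaction". That model serves a different endpoint, so the two sections do not contradict each other.

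**The concern.** A single block in the ratio 5:3 needs eight subjects, which is a whole cohort. Once the cohort is spread over several sites, such a block never fills at any of them, and the cohort total is the sum of incomplete blocks. Smaller mixed blocks reduce the variation without removing it. The stated method therefore need not deliver the stated allocation, and a cohort may have too few placebo subjects for a comparison within that cohort.

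The second point concerns the model. The cohorts run one after another, so a change over time in the population, the procedure or the assay is shared by everyone in a cohort. If all cohorts are 5:3, leaving cohort out puts that shift into the residual variance: the test becomes conservative and loses power. If the ratio differs between cohorts, the shift is also partly confounded with treatment in that trial. Unequal ratios can arise even with exact 5:3 lists, because Protocol 6.3 lets the DSMB place additional subjects at another dose level or change the allocation.

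**Working it through.** **The plan's own figure.** Protocol 6.2 and SAP 4.1 give power 0.851 for 15 against 9 (two-sided t-test, alpha 0.05, 27% change). The SD is not stated, so I solved for the standardised effect d. With noncentrality d/√(1/15 + 1/9) and 22 df, power 0.851 gives d = 1.324, an implied CV of 27%/1.324 = 20.4%. This d reproduces all nine table cells within 0.001, so the table is internally consistent; what it needs is a 15:9 split.

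**Part 1: allocation.** Block size is not given, so three schemes were assumed, each summing to 5:3: one block of 8; blocks of 3 (2:1) and 5 (3:2) in random order; blocks of 2 (1:1), 3 and 3 (2:1 each) in random order. Six site splits of a cohort were used: 3/3/2, 4/2/2, 6/1/1, 2/2/2/2, 2/2/2/1/1 and 2/2/1/1/1/1. Each site starts a fresh list in each cohort.

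Worked case: five sites (2/2/2/1/1), block of 8.

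- Placebo count at a site with two subjects: 0, 1, 2 with probability 10/28, 15/28, 3/28.
- At a site with one subject: 0, 1 with probability 5/8, 3/8.
- Three two-subject sites together: 0, 1, 2, 3 placebo with weights 1000, 4500, 7650, 6075 over 28³ = 21,952.
- Two one-subject sites together: 0, 1, 2 placebo with weights 25, 30, 9 over 64.
- P(exactly 3 placebo) = (6075×25 + 7650×30 + 4500×9)/(21,952×64) = 421,875/1,404,928 = 0.30.
- P(at most 1 placebo) = (1000×25 + 4500×25 + 1000×30)/1,404,928 = 167,500/1,404,928 = 0.12.

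| Block scheme | Exact 5:3, five sites | Exact 5:3, all six splits | At most 1 placebo, five sites |
|---|---|---|---|
| 8 | 30% | 29-41% | 12% |
| 3+5 | 34% | 31-49% | 10% |
| 2+3+3 | 39% | 34-66% | 5% |

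Over all 18 settings:

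- at most one placebo in 0-13% of cohorts, and at least one such cohort in 0-33% of trials;
- all three cohorts exact in 3-29% of trials;
- total 15:9 in 17-40% of trials;
- mean power 0.830-0.849, and below 0.80 in 0.5-14% of trials (for example 0.804 at 17:7 and 0.766 at 18:6).

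If site lists instead carry over from one cohort to the next, 15:9 is met in 24-66% of trials and all three cohorts are exact in 3-15%.

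**Part 2: the model.** Simulation with n = 24, exact 5:3, treatment plus random age and sex with no effect, with and without cohort. Linear drift per cohort is an assumption, since the documents give none. Drift of δ per cohort adds 2δ²/3 to a residual variance of 1 when cohort is omitted: 0.06 at δ = 0.3, 0.17 at 0.5 and 0.67 at 1.0. The monotone case uses 0.5, 1 and 1.5 times d, because Protocol 6.2 and SAP 4 name a monotonic dose response as the analytic goal. Entries are power without/with the cohort term.

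| Drift per cohort | Equal effect | Monotone, drift in the drug's direction | Monotone, drift against it |
|---|---|---|---|
| 0 | 0.82/0.81 | 0.76/0.79 | 0.76/0.79 |
| 0.3 SD | 0.79/0.80 | 0.68/0.78 | 0.78/0.77 |
| 0.5 SD | 0.76/0.81 | 0.62/0.78 | 0.79/0.78 |
| 1.0 SD | 0.60/0.80 | 0.40/0.78 | 0.73/0.79 |

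Type I error without the term at drifts of 0, 0.3, 0.5 and 1.0 SD is 0.051, 0.043, 0.037 and 0.015.

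Illustration with unequal ratios, 4:4, 5:3, 7:1, and 0.5 SD drift. Number the cohorts 0, 1, 2. The mean cohort number is (5 + 14)/16 = 1.1875 on active and (3 + 2)/8 = 0.625 on placebo. The bias without the term is 0.5 × 0.5625 = 0.28 SD; simulated type I error is 0.071. With the term the bias is 0 and the type I error 0.050. Averaged over random splits, type I error without the term is 0.037-0.049.

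**The case against.** The 5 and 3 per cohort are fixed numbers that any list must meet, so a central cap may exist unstated, and block details are rightly kept out of a public protocol. Exact 5:3 is also a strict yardstick: 75-99% of cohorts fall within one subject of it, and no placebo at all occurs in at most 2%. If one site fills a cohort with a block of 8, 5:3 is certain. Mean power stays above 80%, and the primary analysis pools the cohorts.

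On the model, the drift is assumed. The larger gains under equal effects need 0.5-1.0 SD per cohort, that is 1-2 SD from first to last cohort, or about 20-41% of mean FSR at a CV of 20.4%. The 4:4, 5:3, 7:1 sequence has probability of at most 0.7% in any setting; at active counts of 4, 5, 6 with 0.5 SD drift, type I error is 0.054 with or without the term. The stated purpose of the DSMB option is to keep the arms in balance.

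Most of this stands as a limit on size. There is no average type I inflation, overall power loss is small, and no effect on escalation is claimed: the DSMB starts with blinded data (Protocol 16) and no between-arm test governs escalation. It does not remove the points. Neither document requires or cites a cap, and one sentence would supply it. The cohort term follows from the way treatment is assigned and does not depend on proving drift. One further objection also stands: if site remains a stratification factor, neither the SAP model nor the one proposed here contains it.

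**Conclusion.** The concern holds on both parts and should be fixed. As written, the method does not secure 5:3 per cohort: 29-66% of cohorts are exact over the settings tried, and 29-42% with four to six near-even sites under every scheme. Nor does it secure the 15:9 on which the power table rests (17-40% of trials). The cost falls mainly on within-cohort placebo comparisons. These figures assume the block schemes, at least three sites enrolling in each cohort, and no unstated cap.

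The primary FSR model leaves out a factor that is built into the design. The consequence is lost power under drift and, when ratios differ between cohorts, chance confounding in the trial at hand. Its size depends on a drift that the documents do not give: none or slight at 0.3 SD per cohort with equal effects, and substantial at 0.5 SD or more, or when a monotone effect and the drift run the same way.

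**What to change.** 1. In Protocol 6.1 and SAP 3, replace the site-stratified blocks with central randomisation stratified by dose cohort, with 5:3 enforced at cohort level. If site stratification is kept, state a central cap on each arm per cohort. Put block sizes, list structure and the handling of replacements in a restricted randomisation specification held by unblinded staff. It should cover replacements whom the DSMB places at another dose level, and a new list for the remaining subjects if the DSMB changes the ratio. The 5:3 is already in the protocol, so the blind loses nothing new.
2. In SAP 5.1.3, make the primary FSR model treatment, dose cohort (three-level fixed effect, defined by the cohort list from which the subject was randomised), age and gender.

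The cost is a change to the randomisation text, one restricted document and one model term. There is no formal site balance under the first option, and the last assignments in a cohort become somewhat more predictable. The cohort term uses 2 df: power goes from 0.848 to 0.844 on df alone (d = 1.324, 20 against 18 residual df), about 0.01 in simulation with no drift, and about 0.01 when moderate drift opposes a monotone effect.

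If two active replacements are placed one level lower (FSR sets 5:3, 7:3, 3:3), the term costs 0.02 with no drift (0.81 to 0.79). At 0.5 SD drift in the drug's direction it raises power from 0.73 to 0.79. Without the first change it costs 0.02-0.04 with no drift and gains 0.02-0.04 at 0.5 SD, so the two changes should be made together.
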